The randomized clinical trial of adding weekly PRO

Design and setting

The main part of the study consists of a multicenter randomized trial in order to assess the effects of the weekly PRO intervention. The design follows the overall setup presented in the publication by Denis et al, however, adapted to a Danish setting, as described above, including the Danish guidelines for evaluating CT scan in both arms². The randomization and baseline data collection will be made in the IT system (AmbuFlex) by the oncologist at the time of enrollment.

Implementation of the intervention

The intervention is illustrated in Figure 1. *In the experimental arm*, patients will be asked to fill in the PRO questionnaire every week via an internet connection, and they will also be asked to fill in HRQoL questionnaires at any outpatient attendance. However, if their weekly reported symptoms result in a notification, the clinician will contact the patient, and after verification of symptoms, schedule a visit at the clinic for physical examination and evaluation. If relapse or progression of disease is suspected an extra CT scan will be made, otherwise the patient will continue response evaluation/follow-up according to the usual schedule. The clinicians are allowed to reschedule the CT scan based on the phone call alone.

Both the HRQoL measurements and the web application will be administered through a web page that is designed for use on mobile phones, tablets and laptops(AmbuFlex¹⁹). The data will automatically be transferred in real time to a computer server, where notifications are generated and sent to clinicians if the prespecified symptom thresholds are exceeded. Data is automatically scored and will be available in easily interpretable visual reports in the AmbuFlex system.

If participants do not fill in the web-based questionnaire at pre-specified times, a reminder will be sent using a text message to their mobile phone and a message will appear for the clinical staff at the daily notification list.

[figure not shown]

Figure 1. Flow-chart showing the PRO-intervention in the randomized clinical trial.

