To examine the participants quality of life during the study period and at the time of relapse/progressive disease, patients in both arms will be asked to fill in the health-related quality of life (HRQoL) questionnaire every 2 months. The HRQoL questionnaires used are the EORTC QoL-30/LC13 and HADS questionnaire. EORTC-QoL-30 is a questionnaire containing 30 questions with five functional scales (physical function, role function, cognitive function, emotional function and social

function), three symptom scales (tiredness, nausea/vomiting, pain), a global health question and questions regarding frequent symptoms among cancer patients, such as dyspnea, sleep disturbances, loss of appetite, obstipation and diarrhea. The EORTC-QoL-30 also contains a question about financial difficulties. All scales will be linearly transferred to a score between 0-100. For functional scales and global health question, a score of 100 represents the best possible function, while a score of 100 on a symptom scale represents the worst possible symptom. A change in the score by 10 or more is considered a clinically significant change²⁰. LC13 is a supplementary questionnaire to the QLQ-C30 and includes 13 lung cancer-specific questions.

The HADS (The hospital anxiety and depression scale) is a fourteen-item scale. Seven items relate to depression and seven to anxiety. The tool has been developed for detection of anxiety and depression in patients with physical health problems. All items are scored from 0-3 with a possible total score between 0 and 21 for anxiety and depression respectively⁸.

Bjelland et al²¹ identified, in a systematic review, a cut-off point of 8/21 for anxiety or depression. For anxiety, the specificity was 0.78 and the sensitivity 0.9. For depression a specificity of 0.79 and a sensitivity of 0.83 was determined.

The generic EQ-5D-5L⁷ questionnaire will be used to assess quality-adjusted life years (QALY) for a health economic evaluation (*see statistics for details*).

Study design

The study is a multicenter randomised phase III study. After signing informed consent, the patient will be randomized in 1:1 fashion, to the *standard of care arm*, with planned CT-scans according to a standard schedule and measurement of quality of life every 2 months, or to the *experimental arm*, adding weekly PRO monitoring and quality of life measurements to standard of care.

Study population

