Patient enrolment is always when the patients are informed of the results of their first evaluation scan after treatment induction. Patients with stable disease or better response, as described, are eligible.

- In case of treatment end (planned or discontinued) at the time of enrolment, the patient will be included prior to standard follow-up

- In case of ongoing treatment, the patient will be included and continue treatment as scheduled with standard CT based response evaluations
- In the case of local treatment of oligometastatic disease or palliative radiotherapy, the patient will be included if there is no sign of relapse/progression at first evaluation CT scan after treatment and continue follow-up

Inclusion procedure

The patient will have to sign an informed consent at enrolment. The National Committee on Health Research Ethics has been requested and the study does not require approval. Time for consideration before the submission of informed consent is therefore not required and the patient can be enrolled immediately at attendance. Information regarding the study and login procedures for the weekly PRO questionnaire will be provided.

Evaluation criteria

All baseline CT-scans will be evaluated at each site by usual practice. Health-related quality of life (HRQoL) during the observation period will be measured using EORTC QOL-C30/LC13 and HADS. The HRQoL questionnaires including the EQ-5D-5L will be filled in at baseline at randomisation and at every 2 months. The questionnaires will be electronically answered via the AmbuFlex system.

Study plan

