The study plan for the randomized clinical trial is outlined in Table I. In the standard arm, all patients will be followed with CT-scan with the standard of care intervals and asked to fill in the web-based HRQoL questionnaires every 2 months. In the experimental arm, patients will additionally be asked to fill in the web-based PRO questionnaire on a weekly basis. If a detrimental change (See appendix) is noted in the patient's weekly responses to the PRO questionnaire, the patient will be contacted by a study nurse for verification of symptoms. If the symptoms are verified, the patient will be treated by the clinical staff according to standard procedures. If progressive disease is suspected, the patient will have the CT scan rescheduled to as soon as possible. All CT-scans will be described and evaluated by standard practice. It will entirely be up to the treating physician to interpret the results of the CT scans and to define the time of progression as well as the following treatment.

Evaluation at screening, prior to inclusion

The objective of these evaluations is to identify patients, who meet the specified Inclusion- and exclusion criteria. The patient will be informed verbally and in writing. Only patients who have signed informed consent will be included. Following examination and data will be collected prior to inclusion:

- Histological or cytological verification of lung cancer
- Disease stage at treatment start
- Prior treatment and/or maintenance treatment

- Baseline CT scan of the thorax and upper abdomen, showing no signs of progression, after completion of the first treatment for lung cancer, performed within 28 days of randomization.
- Baseline performance status (according to the ECOG's scale¹³), estimated within 14 days of randomization

The patient will be asked to fill in baseline health-related quality of life (EORTC QoL-30/LC13, HADS, EQ-5D-5L) questionnaires via E-Boks immediately after inclusion and then every 2 months.

Additional evaluation for the intervention arm, after inclusion

- Weekly response to the PRO application
- If detrimental changes in PRO responses, earlier evaluation, described above

CT evaluation according to standard follow-up/response evaluation, all participants

- CT-scan of the thorax and upper abdomen, to evaluate the time of progression (or relapse)

Evaluation at relapse or progression

- CT-scan of the thorax and upper abdomen
- Performance status
- Planned 2nd line treatment

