Cost-effectiveness of the PRO application versus standard monitoring is assessed with the incremental cost-effectiveness ratio (ICER), i.e. the ratio of net health care costs to net QALYs (Quality Adjusted Life Years). For a description of the data collection and the analysis, see appendix.

Statistical analysis plan of the Health-Related Quality of Life data

Health-related quality of life (HRQoL) measures are secondary endpoints in the ProWide trial and will be reported in a scientific paper published separately from the main paper. The primary endpoints of the HRQoL paper are Physical function (QLQ-C30), Pain (QLQ C-30), HADS-anxiety and overall EQ-5D-5L index score.

The statistical analyses were planned before any evaluation of the data collected in the trial was made.

Data collection

The HRQoL questionnaires are sent to the patients via the Danish public mail system (eBoks) every second months. All patients in the trial have access to the system. Non-respondents receive a reminder after one week. Responses delivered > 30 days after the invitation is sent is categorized as “missing”.

Specific endpoints of interest in the HRQoL analysis

The specific HRQoL scales that will be analyzed in the ProWide study are:

1. Physical function (QLQ-C30)

Rationale: Physical function is considered a PRO surrogate marker for performance status which is an important prerequisite for both toleration effect of medical antineoplastic treatment.

2. Pain (QLQ C-30)

Rationale: Pain is sensitive to change toward progression in cancer and a symptom that can be managed with analgesics. The symptom could then be improved through actions that are a result of the intervention.

3. HADS-anxiety

Rationale: The intervention could improve the sense of security in the patients and potentially reduce anxiety.

4. EQ-5D-5L index score

Rationale: The generic score represents an overall self-assessed health status and will be used report the effect of the intervention on the overall health.

The EQ-5D-5L score will be reported both in the main paper as a mean-score comparison between the two groups at six months and also analyzed in the HRQoL paper as described below.

HRQoL hypothesis

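### No rule places baseline HRQoL before allocation: an accepted baseline can follow up to 30 days of known allocation and four or five weekly PRO rounds

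*Combined protocol and SAP*

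**What the plan says.** **Order of steps.** Study design: "After signing informed consent, the patient will be randomized in 1:1 fashion". No questionnaire step is named between consent and randomisation. Design and setting: "The randomization and baseline data collection will be made in the IT system (AmbuFlex) by the oncologist at the time of enrollment".

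**Baseline HRQoL.** The section on evaluation at screening lists the data to be gathered before inclusion, with a window of 28 days around randomisation for CT and 14 days for performance status. HRQoL is not on that list. A separate sentence has the patient complete the "questionnaires via E-Boks immediately after inclusion and then every 2 months". Evaluation criteria says that the HRQoL questionnaires "will be filled in at baseline at randomisation and at every 2 months".

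**Acceptance of responses.** SAP, Data collection: "Non-respondents receive a reminder after one week". "Responses delivered > 30 days after the invitation is sent is categorized as" missing. No separate limit is given for baseline.

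**The intervention.** Study plan: "In the experimental arm, patients will additionally be asked to fill in the web-based PRO questionnaire on a weekly basis". Appendix Table 1 marks weekly PRO at baseline for the intervention group only. The day of the first weekly form is not given.

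**Use of baseline.** The SAP section on MID classifies patients as improved, stable or deteriorated against baseline. The primary HRQoL analysis is a linear mixed model with AUC as confirmation, and the SAP does not say how baseline enters either. Appendix sub-study 3 collects the EQ-5D-5L utilities for the QALYs at baseline and every second month.

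**The concern.** A baseline measurement protects a randomised comparison only if allocation cannot have influenced it. Here the form reaches the patient's digital mailbox after inclusion. The documents do not use the term open-label, but they describe no blinding, and a patient who gets a weekly symptom form knows the arm. A patient who answers after the reminder may already have reported symptoms weekly and been contacted by a nurse.

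If that happens, the reference point contains part of what the trial sets out to measure. HADS-anxiety is the most exposed scale, because the SAP's rationale for it is that the intervention may make patients feel more secure. Knowing that one is being monitored, or is not, could move the score within days. The analyses at stake are the MID categories, the QALYs, and the mixed model or AUC if baseline serves as covariate, change-score reference or common starting point.

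**Working it through.** The point rests on a timing rule, and the plan gives no figure of its own to reproduce.

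**1. Can baseline follow allocation?** Consent comes first, then randomisation at enrolment, then HRQoL by E-Boks after inclusion. The wording in Evaluation criteria puts HRQoL at randomisation, not before it. Neither text places the answer before the arm is assigned or disclosed.

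**2. How late can it be?** The reminder goes out at one week, so answers on day 7 or later are foreseen. A response is missing only beyond day 30. If that general rule covers baseline, the maximum delay is 30 days. A two-month interval is 365.25/6 = 60.9 days, and 30/60.9 = 0.49, so the window covers about half the time to the first follow-up form.

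**3. How many weekly rounds can come first?** Weekly time points up to the day of response:

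| Day of baseline response | First round on day 7 | First round on day 0 |
|---|---|---|
| 7 | 1 | 2 |
| 14 | 2 | 3 |
| 21 | 3 | 4 |
| 30 | 4 | 5 |

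**4. What period does a late answer describe?** In the forms printed in the Appendix, QLQ-C30 from item 6 on, LC13 and HADS ask about the past week. After day 7 these items describe only time after randomisation. EQ-5D-5L asks about today, and the first five QLQ-C30 items carry no recall period, so they describe the time of answering.

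**5. What would this do to an estimate?** This step is illustrative, because the documents give neither response delays nor early effects. Let D be the true arm difference at follow-up and f the share of it already present, on average, at baseline.

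- Change from baseline estimates D(1 − f).
- With baseline as covariate and slope r, the estimate is D(1 − r·f).
- An unadjusted mean at follow-up estimates D, whatever f is.

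Take D = 5 points (the MID for physical function and pain, used only as a scale) and assume r from 0.3 to 0.7:

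| Assumed f | Change from baseline | Baseline-adjusted, r = 0.3 to 0.7 |
|---|---|---|
| 0.10 | 5 × 0.90 = 4.5 | 4.85 to 4.65 |
| 0.25 | 5 × 0.75 = 3.75 | 4.62 to 4.12 |
| 0.50 | 5 × 0.50 = 2.5 | 4.25 to 3.25 |
| −0.10 | 5 × 1.10 = 5.5 | 5.15 to 5.35 |

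The last row is a reaction to allocation that runs against the later effect. It inflates the estimate, so the sign of the bias is open.

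**The case against.** The strongest reply is that the text specific to baseline is tighter than the 30-day rule. It speaks of randomisation and of immediate completion, and Design and setting has baseline data entered in AmbuFlex at enrolment. The 30-day rule was written for forms sent every second month, and most patients may answer the first one the same day. This stands in part. Applying 30 days to baseline is a reading of a general rule, and the documents strictly leave the accepted window for baseline unspecified. It does not remove the point. The data entered by the oncologist need not include forms sent to the patient's mailbox, no tighter limit is stated, and even a same-day answer can come after the arm is known.

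The second reply is that little benefit can exist so early. The SAP expects benefit from reduced deterioration under monitoring across the study period, and its 10-point deterioration in physical function and pain runs to progression, in patients enrolled without progression. That is a fair argument against a large early effect on those two scales. It is weaker for HADS-anxiety.

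Third, the consequences are confined. The EQ-5D-5L comparison in the main paper is of means at six months and does not use baseline as written. Overall survival is untouched. Both statements are correct.

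**Conclusion.** The point holds as a gap in timing that should be closed. Following the plan as written can yield baselines that describe only time after allocation. The maximum exposure is 30 days and four weekly rounds (first form on day 7) or five (first form on day 0). This assumes that the general 30-day rule applies to baseline and that patients know their arm. Typical exposure, direction and amount of bias cannot be estimated from the documents.

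A reader might go further in two ways, and the documents support neither.

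- **A fixed dilution.** If 20% to 40% answered late and half the effect were then present, 0.2 × 0.5 to 0.4 × 0.5 gives 10% to 20%, or 0.15 to 0.30 of 1.5 HADS points. Neither input has a source in the plan. The 1.5 points are a threshold for a patient's change, not an expected arm difference. The figure applies only to change scores and assumes one direction.
- **An over-adjusted model.** The SAP never says that baseline is a covariate or that change scores are modelled. The harm to the mixed model and AUC is therefore conditional, whereas the MID categories use baseline explicitly and the QALYs start from baseline utility.

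**What to change.** Reword Evaluation criteria and the screening section so that baseline HRQoL is completed in AmbuFlex at the enrolment visit, after consent and before randomisation or disclosure of the arm. No weekly round and no day of known allocation can then come before it. The questionnaires already run in that system, so only the order of steps changes. The cost is a longer visit, about 63 items (30 + 13 + 14 + 6), on the day the patient is given scan results.

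For patients already enrolled:

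- Keep the 30-day rule in the main analysis.
- Report the delay from randomisation to baseline response by arm.
- Add a sensitivity analysis limited to baselines within 7 days of randomisation, applied identically in both arms.

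The 7-day limit should remain a sensitivity analysis. It would drop nearly all replies prompted by the one-week reminder, and the SAP rules out multiple imputation. A cut-off tied to the first weekly PRO should not be used: that event exists in one arm only, so it would exclude baselines differently by arm.

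One further SAP sentence should state how baseline enters the mixed model and the AUC, so that the reader can see which results depend on it.

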- Categorization of the performed CT scan as prescheduled as a result of a PRO notification

Study period:

Patients will be followed for two years after inclusion in case of non-progressive disease. In case of progressive disease or relapse, the patient will exit the study. For survival analysis and further evaluation, patients will be followed until death or up to 5 years from inclusion.

Endpoints:

The primary outcome measures that will be compared between the experimental and control arm is overall survival with an observation time of 24 months.

The secondary outcome measures are

- Performance status at the time of progressive disease
- Progression-free survival
- Health-related quality of life
- Cost-effectiveness and hospital resource use and costs
- Type of treatment at the time of progressive disease

Time to progression as well as performance status at progression compared to performance status at enrolment into the study may be used to investigate, whether the intervention leads to earlier detection of and better performance status at the time of progression. Quality of life differences may provide insights on possible other patient perceived benefits to the web-mediated follow-up.

Sub-studies

A parallel research project has been financed and will focus on benefit in terms of quality of life and better patient involvement through qualitative interviews with patients included in the study. With qualitative interviews, we aim to describe how participants experience the web-based PRO application and to explore the mechanisms of action related to PROs as a mean of patient involvement. Moreover, we aim at exploring how the intervention influences patients' fear of cancer recurrence and their psychosocial well-being. We will apply the method of an interpretive description as an inductive, flexible research strategy to generate knowledge relevant within a clinical context²². Individual semi-structured interviews will be conducted with 8-10 patients from each arm. After one year, follow-up interviews will be conducted with the same participants in order to explore transformations in the patients' experiences and give new insights in barriers and opportunities for patient involvement in follow up of lung cancer (For details, see appendix, sub-study 1).

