Generalizability of any study finding is important when considering future implementation processes. Previous trials of behavioural interventions among cancer patients have found that patients who choose not to participate have lower education and income, are more often single and have lower survival compared to participants²³⁻²⁵. In another parallel study, we will use registry data and baseline health-related quality of life to compare differences between participants versus non-participant. The aim is to assess differences in their lung cancer disease, symptom- and comorbidity burden, and socioeconomic characteristic. By understanding these differences, we hope to be able to improve future planning of PRO use in lung cancer follow-up for all patients (See appendix for details, sub-study 2).

Intervention costs, and the derived hospital resource use and costs (number of contacts, visits, scans etc.) can be used to estimate the difference in costs in the two arms. Data will be collected retrospectively upon completion of the trial (see Appendix, sub-study 3). Together with information on effects regarding the other endpoints (including health-related quality of life), this can provide a basis for a health economic evaluation of the intervention.

Data collection and analysis

Baseline information on age, gender, Charlson's comorbidity index (extracted from central registry), histology (extracted from the pathology database), TNM stage and treatment type will be noted. During the study period, the number of CT scans will be recorded, as well as disease status and deaths including the cause of death. After verification of progressive disease, the following cancer treatment modalities will be registered. Data will be filed in and stored electronically using the AmbuFlex system and transferred to REDCap (Research Electronic Data Capture) for further data management.

Data on resource use and costs for the health economic evaluation will be collected as a retrospective study upon completion of the trial, using 1) expert assessment for time and material spent on the intervention and 2) individual patient cost data

extracted from the National Patient Registry linked to the National Cost Database (See appendix).

Power calculation

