APPENDIX

Table 1. Study plan for the randomized clinical trial testing weekly PRO responses

	At baseline	At every CT eval.	At progression*
Histology	(x)		
Disease stage	x		
Charlson's comorbidity index	(x)		
Prior treatment	x		
Maintenance treatment	x		
Clinical examination	x	x	x
Performance status	x		x
Quality of life (every 2 months)	x		
CT-scan	x	-	-
Treatment type after progression			x
Weekly PRO (only the intervention group)	x	-	-

* Patients exit the study when progressive disease has been determined
 (x) data is extracted from central registry

EORTC QLQ-C30 (version 3.0)

Vi er interesserede i at vide noget om Dem og Deres helbred. Vær venlig at besvare alle spørgsmålene selv ved at sætte en ring omkring det svar (tal), som passer bedst på Dem. Der er ingen "rigtige" eller "forkerte" svar. De oplysninger, som De giver os, vil forblive strengt fortrolige.

	Slet ikke	Lidt	En del	Meget
1. Har De nogen vanskeligheder ved at udføre anstrengende aktiviteter, som f.eks. at bære en tung indkøbstaske eller en kuffert?	1	2	3	4
2. Har De nogen vanskeligheder ved at gå en lang tur?	1	2	3	4
3. Har De nogen vanskeligheder ved at gå en kort tur udendørs?	1	2	3	4
4. Er De nødt til at ligge i sengen eller at sidde i en stol om dagen?	1	2	3	4
5. Har De brug for hjælp til at spise, tage tøj på, vaske Dem eller gå på toiletet?	1	2	3	4

I den forløbne uge:

	Slet ikke	Lidt	En del	Meget
6. Var De begrænset i udførelsen af enten Deres arbejde eller andre daglige aktiviteter?	1	2	3	4
7. Var De begrænset i at dyrke Deres hobbyer eller andre fritidsaktiviteter?	1	2	3	4
8. Havde De åndenød?	1	2	3	4
9. Har De haft smerter?	1	2	3	4
10. Havde De brug for at hvile Dem?	1	2	3	4
11. Har De haft besvær med at sove?	1	2	3	4
12. Har De følt Dem svag?	1	2	3	4
13. Har De savnet appetit?	1	2	3	4
14. Har De haft kvalme?	1	2	3	4
15. Har De kastet op?	1	2	3	4

I den forløbne uge:

	Slet ikke	Lidt	En del	Meget
16. Har De haft forstoppelse?	1	2	3	4
17. Har De haft diarré (tynd mave)?	1	2	3	4
18. Var De træt?	1	2	3	4
19. Vanskeliggjorde smerter Deres daglige gøremål?	1	2	3	4
20. Har De haft svært ved at koncentrere Dem om ting som f.eks. at læse avis eller se fjernsyn?	1	2	3	4
21. Følte De Dem anspændt?	1	2	3	4
22. Var De bekymret?	1	2	3	4
23. Følte De Dem irriteret?	1	2	3	4
24. Følte De Dem deprimeret?	1	2	3	4
25. Har De haft svært ved at huske?	1	2	3	4
26. Har Deres fysiske tilstand eller medicinske behandling vanskeliggjort Deres familieliv ?	1	2	3	4

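### Performance status and treatment at progression exist only for documented progressors, a set formed after randomisation, and the plan gives no analysis set or rule for deaths that come first

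*Combined protocol and SAP*

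**What the plan says.** The Endpoints section of the protocol lists among the secondary outcomes "Performance status at the time of progressive disease" and "Type of treatment at the time of progressive disease". On their use it says only: "Time to progression as well as performance status at progression compared to performance status at enrolment into the study may be used to investigate". The stated questions are if weekly monitoring brings detection forward and if patients then have better performance status (PS) at progression.

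The data schedule is narrow. Table 1 in the Appendix marks PS at baseline and at progression. It leaves PS blank at CT evaluations, although clinical examination is marked there. The table's footnote reads "Patients exit the study when progressive disease has been determined". Under Data collection and analysis, "After verification of progressive disease, the following cancer treatment modalities will be registered". The same section records disease status "as well as disease status and deaths including the cause of death", but nothing links deaths to these two endpoints.

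Under Study plan, a verified notification in the experimental arm can bring the scan forward: "If progressive disease is suspected, the patient will have the CT scan rescheduled to as soon as possible". The date of progression is a local clinical decision: "It will entirely be up to the treating physician to interpret the results of the CT scans and to define the time of progression".

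The Statistics section names a log-rank test in all randomised patients for overall survival, and Cox regression for time-to-event outcomes. It names no method, analysis set or handling of death for PS or treatment type.

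**The concern.** Two separate problems affect what these endpoints can show.

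- **Selection.** Patients who deteriorate and die before a scan documents progression have the worst outcome and contribute no value. If weekly monitoring turns some of these deaths into documented progressions, it adds sicker patients to the experimental arm's progressors and makes that arm look worse than it is.
- **Lead time.** PS is taken earlier in the disease course in the arm whose scans can be moved forward. Where PS declines over time, this favours the experimental arm even if no patient is in better condition on any given day.

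The protocol's introduction explains the survival gain in the French trial by earlier detection, better PS and earlier second treatment. A PS difference here will naturally be read as evidence for that chain.

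**Working it through.** **1. Who has a value** (Study plan; Study period; Data collection and analysis; Table 1)

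| Course within two years | PS at progression | Treatment at progression |
|---|---|---|
| Progression documented | recorded | recorded |
| Death, no documented progression | none (death and cause recorded) | none |
| Alive, progression-free | none | none |

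The only set with data is the documented progressors.

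**2. The plan's own figures.** No size or power is stated for either endpoint. The overall-survival figure reproduces: 50% against 63.2% at one year gives HR = ln(0.632)/ln(0.50) = 0.662. A two-proportion calculation (two-sided 5%, 80% power) gives 221 per arm, and 221/0.90 = 245.6, so 246 per arm and 492 in total. The 246 is used below.

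**3. Selection.** Let *u* be the share of first events that are deaths without documented progression, *q* the share with PS 0-1 among documented progressors, and *p* the share with PS 0-1 over all first events. Then *p* = *q*(1 − *u*). The documents give none of these rates.

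Assume *q* = 0.60 in both arms, so that progressors alone show no difference:

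| *u* control / experimental | *p* control | *p* experimental | Hidden difference |
|---|---|---|---|
| 10% / 5% | 0.60 × 0.90 = 54% | 0.60 × 0.95 = 57% | 3 points |
| 20% / 10% | 0.60 × 0.80 = 48% | 0.60 × 0.90 = 54% | 6 points |

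Conversely, assume *p* = 0.60 in both arms. Progressors alone then show *q* = 0.60/(1 − *u*):

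| *u* control / experimental | *q* control | *q* experimental | Apparent difference |
|---|---|---|---|
| 15% / 5% | 70.6% | 63.2% | −7.4 points |
| 20% / 10% | 75.0% | 66.7% | −8.3 points |
| 30% / 15% | 85.7% | 70.6% | −15.1 points |

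For scale, if 85% of 246 patients have a first event (209 per arm, also assumed), the standard error at 54% against 57% is √[(0.54 × 0.46 + 0.57 × 0.43)/209] = 4.9 points. The hidden 3 and 6 points are then about 0.6 and 1.2 standard errors.

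**4. Lead time.** The Background gives scan intervals of 8, 9 or 12 weeks on maintenance. If progression were found only at scheduled scans and began evenly across the interval, the mean wait would be half of that: 4, 4.5 or 6 weeks. The mean lead cannot exceed this wait. The documents do not say what fraction would be gained.

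A simulation gave both arms the same disease course and the same deaths, and moved only the detection date. Assumptions, none from the documents: exponential times; medians of 5 months to progression, 2 or 4 months from progression to poor PS, and 4 months from poor PS to death; scans every 8 or 12 weeks; every progression in the experimental arm found earlier by the stated lead, but never before onset. One-year survival was 59% to 70%.

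| Lead | Good PS among progressors, experimental minus control | Same, deaths without documented progression counted as poor |
|---|---|---|
| 2 weeks | +5.1 to +9.7 points | +6.0 to +10.7 points |
| 4 weeks | +9.5 to +17.5 points | +10.8 to +19.3 points |
| 6 weeks | +12.6 to +23.0 points | +13.9 to +26.0 points |

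The true effect on PS and death is zero throughout. Counting deaths as the worst outcome therefore deals with selection but leaves lead time in place.

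**The case against.** The strongest reply is that being found earlier, in better PS, is what the trial sets out to test; the Endpoints section says so. For that question lead time is the intended result. It misleads only if it is taken as slower decline or patient benefit, and the plan does not claim that. Benefit is judged on overall survival in all randomised patients. This stands, and it limits the lead-time point to one of interpretation. It does not answer the selection problem.

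Nor does the plan state that these endpoints will be tested among progressors only. The comparison is inferred, although the schedule supports no other. The accurate criticism is that the analysis is unspecified and that the only one available is open to bias.

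The sizes are soft. The hidden differences of 3 and 6 points are about one standard error. The simulation gives every experimental-arm progression the full lead, while not every progression will trigger a notification. Control patients may also be found through symptoms: the health-economic appendix describes non-systematic symptom reporting and telephone contact in that arm.

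Partial handling exists. PS at progression is to be compared with PS at enrolment, and QLQ-C30 physical function, named as a surrogate for PS, is collected every two months in both arms. The first corrects neither problem. The second helps only while patients remain in the study.

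A reader might infer that lead time could also hide a benefit. It cannot: it pushes towards the experimental arm and could mask only a harm. Hidden benefit comes from selection.

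**Conclusion.** The concern holds for two secondary endpoints. PS and treatment type at progression have data only for a group formed after randomisation, which the intervention can alter, and no rule covers deaths before documented progression. The directions follow from the design: selection can hide a benefit, and lead time favours the experimental arm. The sizes do not. The 3 to 6 points hidden, and the 5 to 10 points created by a two-week lead, rest on assumed rates, and the documents give neither a rate of undocumented death nor an expected lead.

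A reader might go further and conclude that the main result is compromised. The documents do not support that: overall survival is compared from randomisation in everyone randomised and does not depend on when progression is found. What is at risk is the explanation offered for a survival result. The change should be made, because most of it uses data already collected.

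**What to change.** 1. Analyse PS at first event (progression or death) as an ordinal outcome, with death without documented progression as the worst category, adjusted for baseline PS. Keep the progressor-only figure as descriptive. Report by arm how many patients are alive and progression-free at two years, since they still contribute no value.
2. Report second-line treatment with all randomised patients as the denominator, for example as cumulative incidence from randomisation with death as a competing event.
3. State that neither step removes lead time, so a PS difference at progression is to be read as earlier detection and not as slower decline. Name two-monthly QLQ-C30 physical function as supporting evidence at fixed times while patients remain in the study. The plan already limits that analysis to 12 months and to time points with at least 50% compliance in both arms.

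Recording PS at scheduled CT visits would not give a fixed-time comparison: patients leave at progression, so later values would come only from non-progressors, and scan intervals differ by treatment.

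The cost is analysis-plan wording, with no new data collection. The downside is that the ordinal outcome mixes PS with early death, including deaths not due to lung cancer. Cause of death is recorded, so a sensitivity analysis can treat those separately.
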